**Table 7 Drugs to be used with caution while on study**

Category	Drug Names
CYP3A substrates with narrow therapeutic index	alfentanil, cyclosporine, diergotamine, dihydroergotamine, ergotamine, fentanyl, sirolimus, tacrolimus, terfenadine, warfarin sodium or any other coumadin-derivative anticoagulants, direct thrombin inhibitors (eg, argatroban), and Factor Xa inhibitors (eg, rivaroxaban)
Moderate inhibitors of CYP3A4	amprenavir, aprepitant, atazanavir, cannabinoids, casopitant, cimetidine, ciprofloxacin, darunavir, diltiazem, fosamprenavir, imatinib, metronidazole, Schisandra sphenanthera, sertraline, suboxone, tofisopam, verapamil, zafirlukast
Moderate inducers of CYP3A4	bosentan, cotrimoxazole, efavirenz, etravirine, ethosuximide, genistein, metyrapone, mexiletine, modafinil, nafcillin, talviraline, tipranavir
Medications which alter the pH of the GI tract a,b	antacids, H 2 antagonists (eg, ranitidine), proton-pump inhibitors (eg, omeprazole)
Medications that have possible risk of TdP/QT prolongation	alfuzosin, amantadine, atazanavir, chloral hydrate, clozapine, dolasetron, eribulin, famotidine, felbamate, fingolimod, foscarnet, fosphenytoin, gatifloxacin, gemifloxacin, granisetron, iloperidone, indapamide, isradipine, lapatinib, lithium, moexipril, nicardipine, nilotinib, octreotide, ofloxacin, oxytocin, paliperidone, pasireotide, quetiapine, ranolazine, risperidone, roxithromycin, sertindole, sunitinib, tamoxifen, tizanidine, vardenafil, venlafaxine, ziprasidone
Medications that have conditional risk of TdP/QT prolongation	amitriptyline, amisulpride, ciprofloxacin, clomipramine, desipramine, diphenhydramine, doxepin, fluoxetine, galantamine, imipramine, nortriptyline, paroxetine, protriptyline, sertraline, solifenacin, trazodone, trimethoprim-sulfa, trimipramine

Category	Drug Names
BCRP substrates	atorvastatin, irinotecan, methotrexate, rosuvastatin, simvastatin, sulfasalazine, topotecan

Abbreviations: BCRP, breast cancer resistance protein; CYP, cytochrome p; FDA, Food and Drug Administration; GI, gastrointestinal; TdP, Torsades de Pointes

a Infigratinib should be dosed at least 2 hours before or 10 hours after dosing with a gastric protection agent.

b If possible, proton pump inhibitors should be avoided due to their long pharmacodynamic effect and replaced with H2 antagonists or antacids.

Sources: [FDA Guidance for Industry, 2017](#); [Flockhart 2007](#); drugbank.ca.

#### 6.4.1.1.1 CORTICOSTEROIDS

Chronic dosing of corticosteroids such as dexamethasone and prednisone is known to induce CYP3A enzymes, thereby increasing the risk of reducing drug exposure to sub-therapeutic levels. In addition infigratinib is an in vitro inhibitor of CYP3A4 and has the potential to increase the systemic exposure of corticosteroids that are metabolized by CYP3A4.

Systemic corticosteroid treatment can be used with caution. If possible, the participant should be on a stable dose for at least 2 weeks prior to study entry.

#### 6.4.1.2 PROHIBITED CONCOMITANT THERAPY

A concomitant medication is considered prohibited if it appears on any of the prohibited medication lists for any clinical pharmacology property of the drug (eg, CYP, BCRP).

Details for specific medications prohibited while on study are provided in [Table 8](#). The rationale for the restricted medications is provided below.

Other investigational therapies must not be used while the participant is on the study. Anticancer therapy (chemotherapy, biologic or radiation therapy, and surgery) other than the study drug must not be given to participants while the participant is on study drug. If such agents are required, then the participant must be discontinued from study drug. The only exception is palliative localized radiation therapy for bone metastases with approval by QED Therapeutics' medical monitor.

Strong inhibitors of CYP3A4 such as the ones listed in [Table 8](#) are prohibited because infigratinib is a likely substrate of this isoenzyme.

Strong inducers of CYP3A4 are prohibited because their usage may decrease the exposure of infigratinib. Therefore, agents such as those listed in [Table 8](#) are prohibited. Please note that the list may not be exhaustive.

Subjects must also avoid the consumption of grapefruits, grapefruit juice, grapefruit hybrids, pomegranates, star fruits, pomelos, Seville oranges or juice within 7 days prior to the first dose of infigratinib and throughout the treatment period due to a potential CYP3A4 interaction with study drug.

Medications that increase the serum levels of phosphorus and/or calcium are prohibited.

A Phase 0 Study of Infigratinib in Recurrent Glioblastoma Patients  
Protocol 2020-08

prolong the QT/QTc interval or induce TdP (risk of TdP/QT prolongation) are prohibited. List of these medications is given in [Table 8](#). Please note that the list might not be comprehensive.

**Table 8 List of prohibited medications and substances while on study**

Category	Drug Names
Strong inhibitors of CYP3A4	clarithromycin, conivaptan, fluconazole, fluvoxamine, indinavir, itraconazole, ketoconazole, lopinavir, mibepradil, miconazole, nefazodone, nefinavir, norfloxacin, posaconazole, ritonavir, saquinavir, telithromycin, voriconazole  grapefruit, grapefruit juice, grapefruit hybrids, pomegranates, star fruits, pomelos, Seville oranges or products containing juice of these fruits
Strong inducers of CYP3A4	avasimibe, carbamazepine, nevirapine, phenobarbital, phenytoin, pioglitazone, primidone, rifabutin, rifampin, St. John's wort, troglitazone
Medications which increase serum phosphorus and/or calcium	calcium, parathyroid hormone, phosphate, vitamin D (including multivitamins containing vitamin D)
Medications with established potential for QT prolongation or TdP	amiodarone, anagrelide, arsenic trioxide, astemizole (off US market), azithromycin, bepridil (off US market), chloroquine, chlorpromazine, cisapride (off US market), citalopram, clarithromycin, cocaine, disopyramide, dofetilide, domperidone (not on US market), dronedarone, droperidol, erythromycin, escitalopram, flecainide, halofantrine, haloperidol, ibutilide, levofloxacin, levomethadyl (off US market), mesoridazine (off US market), methadone, moxifloxacin, ondansetron, pentamidine, pimozide, probucol (off US market), procainamide (oral off US market), quinidine, sevoflurane, sotalol, sparfloxacin (off US market), sulpiride (not on US market), terfenadine (off US market), thioridazine, vandetanib
Abbreviations: CYP, cytochrome p; TdP, Torsades de Pointes; US, United States	

#### 6.4.1.3 SUPPORTIVE CARE

Participants should receive full supportive care. Participants are instructed to maintain adequate oral hydration at home, in order to prevent dehydration secondary to vomiting and diarrhea. During visits, participants should be evaluated for signs and symptoms of dehydration and, if necessary, intravenous hydration should be implemented at the discretion of the investigator.

##### 6.4.1.3.1 SUPPORTIVE MANAGEMENT FOR DIARRHEA

Participants should receive instructions on the management of diarrhea. In the event of diarrhea (Section 6.1.3), supportive measures should be initiated as early as possible. These include the following:

- At the first sign of loose stools, the participant should initiate anti-diarrheal therapy (for example, loperamide) and notify the investigator/site for further instructions and appropriate follow-up.

A Phase 0 Study of Infigratinib in Recurrent Glioblastoma Patients  
Protocol 2020-08

- Participants should also be encouraged to drink fluids (for example, 8 to 10 glasses of clear liquids per day).
- Site personnel should assess response within 24 hours.
- If diarrhea does not resolve with anti-diarrheal therapy within 48 hours to either baseline or Grade 1, the participant should be seen at the investigational site for further evaluation and management per institutional guidelines.
- Refer to [6.1.3](#) for additional information for diarrhea management and dose modification.

In severe cases of diarrhea, the measurement of neutrophil counts and body temperature and proactive management of diarrhea with antidiarrheal agents should be considered.

If diarrhea is severe (requiring IV rehydration) and/or associated with fever or severe neutropenia, broad-spectrum antibiotics such as fluoroquinolones must be prescribed.

Participants with severe diarrhea or any grade of diarrhea associated with severe nausea or vomiting should be carefully monitored and given intravenous fluid (IV hydration) and electrolyte replacement.

When therapy with antidiarrheal agents does not control diarrhea to tolerable levels, study treatment should be temporarily interrupted, dose reduced, or permanently discontinued per [6.1.3](#).

#### [6.4.1.3.2 SUPPORTIVE MANAGEMENT RECOMMENDATIONS FOR NAUSEA AND VOMITING](#)

---

Recommended antiemetic treatment should follow current guidelines for high/moderate emetic risk agents, such as consensus-based guidelines from the National Comprehensive Cancer Network but is left to investigator's discretion based on participant characteristics and local medical practices. Note: ondansetron is listed as a prohibited medication but may be used at the investigator's discretion.

Current recommendation for antiemetic treatment consists of a 5-HT3 receptor antagonist and should be given prior to starting study drug (continue daily, choose 1):

- Ondansetron 8-16 mg (total dose) PO daily
- Dolasetron 100 mg PO daily, as needed

Breakthrough treatment can be given by adding 1 agent from a different drug class to the current regimen (i.e., olanzapine 5-10 mg PO daily, dexamethasone 12 mg PO/IV daily).

In Phase 0, ondansetron IV may be administered as per routine care or institutional guidelines.

In the event that the investigator believes concomitant antiemetic medication is not necessary in cycles 2+, the antiemetic regimen may be discontinued.

#### [6.4.1.3.3 SUPPORTIVE MANAGEMENT RECOMMENDATIONS FOR HYPERPHOSPHATEMIA](#)

---

Increases in phosphate, a pharmacodynamic effect of infigratinib, can affect the homeostasis of serum phosphorus and serum calcium. As such, within the first week of infigratinib treatment (Expansion Phase), serum phosphorus and calcium levels should be monitored and checked. Manage as clinically indicated with a low phosphate diet, dose modifications/interruption, and phosphate binders. Prophylactic use of a phosphate-binding agent is allowed on days of infigratinib administration per institutional guidelines. Per investigator's discretion, if there is no ongoing hyperphosphatemia during the week with no infigratinib treatment, use of the phosphate binder should be paused. If necessary, infigratinib dosing may be interrupted to allow for normalization of serum levels of phosphorus and calcium and then resumed at a lower dose. Also see [Table 4](#) for toxicity follow-up evaluation.

A Phase 0 Study of Infigratinib in Recurrent Glioblastoma Patients  
Protocol 2020-08

Mild to moderate elevations in serum creatinine have occurred in association with hyperphosphatemia. Subjects should be carefully monitored for electrolyte changes and early signs of renal insufficiency; dosing should be withheld until serum creatinine returns to baseline, Grade 1, or better. Additionally, SAEs of renal failure, nephropathy, and acute kidney injury have been reported. In the event of acute, severe hyperphosphatemia and clinical evidence of emerging calciphylaxis, additional phosphorus-lowering strategies, including hemodialysis, should be considered. ([QED 2019](#))

#### **6.4.1.3.4 SUPPORTIVE MANAGEMENT RECOMMENDATIONS FOR HEMATOPOIETIC GROWTH FACTORS**

---

Prophylactic use of recombinant hematopoietic growth factors may be used per the investigator's discretion and institutional guidelines.

#### **6.4.1.3.5 SUPPORTIVE MANAGEMENT RECOMMENDATIONS FOR OCULAR DISORDER**

---

Infigratinib very commonly causes dry eye and blurred vision; other commonly reported ocular events include conjunctivitis, increased lacrimation, punctate keratitis, and visual impairments. CSC/RPED have also been reported. Subjects should receive dry eye prophylaxis with ocular demulcents as needed.

Ophthalmological examinations (performed by an ophthalmologist) should be done at baseline/screening, phase 0 follow-up, every 3-4 months thereafter, and at any time as per physician discretion for visual symptoms. Withhold infigratinib if central serous chorioretinopathy (CSC)/ retinal pigment epithelial detachment (RPED) occurs and permanently discontinue if it does not resolve after 14 days or if it is Grade 4 in severity. Also discontinue infigratinib for other Grade 4 ocular disorders and for Grade  $\geq 1$  retinal vein occlusion. ([QED 2019](#))

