1.2 SCHEDULE OF ACTIVITIES (SOA)

Procedures	Phase 0							Expansion				Safety Phone Call ~30 days after last dose	Survival Follow Up Phone Call / Letter
	Screening Day -28 to -1	Enrollment/Baseline Day 1	Days 2-5	Pre-surgical Assess. Day 6	Surgical Visit Day 7	Post-op Follow Up ~7 days after last dose	Cycle 1 (28 days) 	Cycle 2 (28 days) 	Subsequent Cycles (28 days) 	End of Study Treatment			
Visit #	1	2	n/a	3	4	5	6-8	9-11	12, 13...	Last	n/a	n/a	
Informed consent	X												
Collect archival/biopsy tissue	X												
Demographics	X												
Medical history	X												
Diagnosis and extent of cancer	X												
Eligibility	X	Pre											
Concomitant medication review	X			X-----X									
Adverse event review and evaluation	X			X-----X							X		
Surgical and medical procedures	X			X-----X									
Phone Call / Letter											Phone	~Q3 months 	
TREATMENT/DRUG ADMINISTRATION													
Administer study drug		QD	QD (Home)	QD	QD		X 	X 	X 				
Review of Home Dosing Diary		X		X	X		1	1	1	X			
Drug Compliance / Accountability		X		X	X		1	1	1	X			
CLINICAL PROCEDURES													
Physical exam	X 										X		
Neurological exam	X 										X		
Brief Physical and Neurological exam						X	1	1	1				
Ophthalmologic Evaluation 	X 					X			C3D1 and every 4 months after	X			
ECOG	X	X				X	1	1	1				
Vital signs	X 			X		X	1	1	1	X			

A Phase 0 Study of Infigratinib in Recurrent Glioblastoma Patients

Protocol 2020-08

	Phase 0								Expansion			Survival Follow Up Phone Call / Letter
	Screening Day -28 to -1	Enrollment/Baseline Day 1	Days 2-5	Pre-surgical Assess. Day 6	Surgical Visit Day 7	Post-op Follow Up ~ 7 days after last dose	Cycle 1 (28 days) 	Cycle 2 (28 days) 	Subsequent Cycles (28 days) 	End of Study Treatment		
Procedures												
Height	X 											
Weight	X 									X		
12-Lead ECG 	X	X		X			1	1	1	X		
Craniotomy					X							
LAB PROCEDURES												
Hematology (CBC w/diff) 	X 						X	1	1	1	X	
Serum chemistry 	X 						X	1	1	1	X	
Pregnancy test 	X 						X	1	1	1	X	
Coagulation 	X 											
Urinalysis 	X 						X	1	1	1	X	

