Diarrhea Grade 1	Maintain dose level of infigratinib, but initiate anti-diarrheal treatment  Note: Antidiarrheal medication is recommended at the first sign of abdominal cramping, loose stools or overt diarrhea. See 6.4.1.3.1

A Phase 0 Study of Infigratinib in Recurrent Glioblastoma Patients  
 Protocol 2020-08

Worst Toxicity CTCAE v5.0 Grade (unless otherwise specified)	Recommended Dose Modifications any time during a cycle of therapy
Grade 2	
Hold dose of infigratinib until resolved to CTCAE Grade <math>\leq 1</math>
 
 
Optimize anti-diarrheal treatment, maintain dose level of infigratinib.
 
For reoccurrence of diarrhea CTCAE Grade 2, hold dose of infigratinib until resolved to CTCAE Grade <math>\leq 1</math>, <math>\downarrow</math> infigratinib by 1 dose level
 

Grade 3	
 
Hold dose of infigratinib until resolved to CTCAE Grade <math>\leq 1</math>
 
Optimize anti-diarrheal treatment
 
<math>\downarrow</math> infigratinib by 1 dose level
 
For reoccurrence of diarrhea CTCAE Grade 3, despite optimal anti-diarrheal treatment, discontinue patient from study treatment.
 

Grade 4	Discontinue patient from study treatment.
Vomiting Grade 2 not controlled by optimal anti-emetic therapy	Hold infigratinib doses until $\leq$ grade 1, $\downarrow$ 1 dose level
Grade 3 not controlled by optimal anti-emetic therapy or Grade 4	Discontinue patient from study
Eye Disorders (confirmed by ophthalmologic examination)	
Retinal disorders Grade 2 CSR and CSR-like events	Hold infigratinib until resolved to $\leq$ grade 1 but refer the patient to a retinal specialist for evaluation 
 
If resolved in <math>\leq 14</math> days, <math>\downarrow</math> infigratinib by 1 dose level
 
If resolved in <math>> 14</math> days, discontinue infigratinib
 

Grade 3 CSR and CSR-like events and any other grade 3 eye disorders	Hold infigratinib until resolved to grade $\leq 1$ . 
 
If resolved in <math>\leq 14</math> days, <math>\downarrow</math> infigratinib by 1 dose level
 
If resolved in <math>> 14</math> days, discontinue infigratinib
 

$\geq$ grade 1 retinal vein occlusion, grade 4 CSR and CSR-like events, and grade 4 other eye disorders	Discontinue infigratinib

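### In the Expansion Phase, section 6.4.1.3.5 and Table 3 give different drug-hold rules for a Grade 1 retinal event, and section 6.4.1.3.5 leaves resolution undefined

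*Combined protocol and SAP*

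**What the plan says.** Section 6.4.1.3.5 (supportive management of ocular disorders) states: "Withhold infigratinib if central serous chorioretinopathy (CSC)/ retinal pigment epithelial detachment (RPED) occurs and permanently discontinue if it does not resolve after 14 days", and adds permanent discontinuation "or if it is Grade 4 in severity". It also stops the drug for other Grade 4 ocular disorders and for retinal vein occlusion of Grade 1 or higher. It gives no dose-reduction rule for restarting.

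Table 3 (section 6.1.3) handles retinal disorders by grade. Its first row is "Grade 2 CSR and CSR-like events", with the instruction "Hold infigratinib until resolved to $\leq$ grade 1 but refer the patient to a retinal specialist for evaluation". The Grade 3 row has the same resolution target. In both rows, reaching that target within 14 days leads to a restart one dose level lower, and taking longer leads to discontinuation. Grade 4 events, and retinal vein occlusion of any grade from 1, lead to discontinuation. There is no Grade 1 row for CSR or CSR-like events.

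Section 6.1.3 allows no dose modifications in Phase 0, so Table 3 applies to the Expansion Phase only. Section 6.4.1.3.5 is not limited to a phase.

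**The concern.** Two sections of one protocol tell a site what to do with the drug when a retinal event is found, and they do not start at the same grade. Two sites could each follow the text and act differently on the same finding. What is at stake is consistent handling of a sight-related toxicity and consistent exposure in a small cohort. Scheduled eye examinations include retinal OCT and dilated fundoscopy (Schedule of Activities, footnote 11; section 8.2.5), so low-grade findings will be looked for systematically.

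**Working it through.** The protocol gives no figure to reproduce here. The check sets the two rules side by side, taking CSC/RPED and CSR/CSR-like events to be the same events.

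| Event in the Expansion Phase | Section 6.4.1.3.5 | Table 3 | Result |
|---|---|---|---|
| Grade 1, new | Withhold | No row, so no hold listed | Differ |
| Grade 1, still present after 14 days | Discontinue permanently | No row | Differ |
| Grade 2 or 3, down to Grade 1 by day 14 and persisting | Depends on the meaning of *resolve* | Restart one level lower | Unclear |
| Grade 2 or 3, still above Grade 1 after 14 days | Discontinue | Discontinue | Agree |
| Grade 4 | Discontinue | Discontinue | Agree |
| Retinal vein occlusion, Grade 1 or higher | Discontinue | Discontinue | Agree |

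**Triggering grade.** Section 6.4.1.3.5 uses grades where it wants a threshold (Grade 4 for CSC/RPED and other ocular disorders, Grade 1 for vein occlusion) but gives none for withholding. Table 3 likewise names Grade 1 for vein occlusion, yet starts CSR at Grade 2. No other row of Table 3 fills the gap: those for other ocular toxicity and for other clinically significant adverse events both start at Grade 3.

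**Meaning of *resolve*.** There are two candidate readings.

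- Complete resolution: row three of the table becomes a permanent stop under section 6.4.1.3.5 and a restart under Table 3.
- Grade 1 or lower, borrowed from Table 3: row three agrees. A Grade 1 event then already meets the target when it is found, so the 14-day stop could never apply to it, although the text still says to withhold.

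Neither reading makes the two sections match in every row.

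**Terminology.** The abbreviation list (section 10.2) defines CSC and RPED but not CSR, and nothing links the terms. If RPED were not counted as CSR-like, a Grade 2 RPED would have no hold in Table 3 either, because other eye disorders enter the table at Grade 3.

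**Precedence.** No text ranks one section above the other. The diarrhea section (6.4.1.3.1) refers to 6.1.3, and the hyperphosphatemia section (6.4.1.3.3) refers to Table 4. The ocular section has no such cross-reference.

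**Scale.** Sections 9.1 and 9.2 give 20 Phase 0 participants with 50% expected to enter the expansion: 0.50 × 20 = 10. One participant handled differently is 1/10 = 10% of that cohort.

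**The case against.** The strongest reply is that Table 3 is silent at Grade 1 and does not say to continue. Where the table means dosing to carry on through a mild event, it says so: Grade 1 diarrhea, Grade 1 and 2 QTcF prolongation, and phosphorus above 5.5 and up to 7.0 mg/dL all carry an instruction to maintain the dose. A site could therefore satisfy both sections by applying 6.4.1.3.5 to what the table leaves open. This stands against any claim that Table 3 orders continued dosing. It does not remove the difference, because nothing tells a site to fill the gap that way, and a site working from Table 3 alone would find no hold.

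The second reply is that section 6.4.1.3.5 may simply be a short form of Table 3, with *resolve* meaning Grade 1 or lower. That is possible, so the Grade 2 and 3 case is an ambiguity and not a proven contradiction.

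A reader might also infer that the 14-day rules differ. They do not: Table 3's retinal rows discontinue after 14 days, and its footnote stops treatment for any dose delay beyond 14 days.

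A reader might further infer that the examination intervals conflict. The Schedule's "C3D1 and every 4 months after" sits within the "every 3-4 months thereafter" of section 6.4.1.3.5. Cycle 3 Day 1 is at most an earlier first check.

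Finally, both places are worded as recommendations, and section 6.1.3 sends dose-reduction questions to the Safety Officer. That softens the consequence but leaves the text unclear.

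**Conclusion.** The point holds for the Expansion Phase. The firm part is the trigger: a Grade 1 event is withheld under section 6.4.1.3.5 and has no hold under Table 3. Permanent discontinuation of a persisting Grade 1 event also follows from section 6.4.1.3.5 if *resolve* carries its ordinary meaning. The Grade 2 and 3 restart question is an ambiguity created by that undefined word. The documents do not support a claim of opposite instructions at every grade.

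The conclusion assumes that the two sets of terms describe the same events. This is the natural reading but is not stated. The protocol reports that CSC/RPED have occurred with the drug but gives no frequency for them, so the number of participants affected cannot be estimated. No sample size, endpoint definition or other statistical figure depends on it. This is an internal inconsistency that is relevant to safety and should be corrected.

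**What to change.** Reconcile section 6.4.1.3.5 and the retinal rows of Table 3 on three items:

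- the grade at which withholding starts, with an explicit entry for Grade 1 in Table 3;
- what *resolve* means for the 14-day rule and for restarting;
- one set of terms for these events, stating whether RPED is included and defining CSR in section 10.2 if it is kept.

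Add a cross-reference stating which of the two governs. The choice of rule belongs to the sponsor and its clinical advisers. The cost is a wording change in one section, a few table rows and possibly one abbreviation, made through a protocol amendment. No redesign or new data collection is needed.
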